Potential participants will be recruited as follows. Billing records from TJUH clinics will be reviewed to identify AAs aged 60+ who have type 2 diabetes. We will obtain the attending physician's permission to contact these patients. We will then mail an introductory letter signed by the PCP (or endocrinologist for patients recruited from the endocrinology clinic) that describes the study and includes a telephone number to call if the patient wishes to participate or opt out. We will also place study brochures and posters in the waiting rooms of the medical recruitment sites.

The letters will be followed by recruitment calls (to patients who did not opt out) from study staff to ascertain study interest. If the patient is interested, study staff will explain the study details and confirm eligibility criteria (e.g., self-report of memory problems). Study staff will administer a brief memory test to screen out patients who are unlikely to have MCI. The memory test will consist of asking patients to recall a list of 12 words. Participants who recall fewer than 5 words will be considered to have possible memory impairment, and will be invited to enroll in the study. The Outcome Assessor will then schedule an in-home visit to obtain informed consent, administer the baseline assessment, and test the participant's A1c level. Within 1 week of this in-home visit, the PI will review the participant's neuropsychological test profile to determine if the participant has MCI, and will confirm that the participant meets all other eligibility criteria.

For participants who meet cognitive and diabetes criteria, the research assistant will contact the participant to discuss the Run-in Phase. Participants will be informed that they will be paid \$10 for each of the two run-in visits. During this call, the RA will review the participants' current oral hypoglycemic medications, and will ask them to identify the one that is prescribed at the highest dosing frequency (this will be referred to as the Target Medication). The Target Medication is the diabetes drug that is selected to be put in the MEMS bottle/cap. The RA will instruct the participant to contact their pharmacy to request 2 copies of the label for the Target Medication. The RA will offer to

Version 4 (Jan 2015)

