The adherence rate will be determined by the percent of pills that were taken on time. The instructions on the pharmacy label will be used to determine the number and timing of pills to be taken each day. If a participant only takes 1 dose daily, and no time is specified on the label, the RA will ask the participant what time they typically take the pill. This time will be designated as the Target Time. If the label indicates that multiple daily doses should be taken (and no time is listed), the participant will be asked for the times that they usually take each dose to determine the Target Time of each dose. If the label specifies specific times, these times will be the Target Times. To be considered as "on time", a pill must be taken within 4 hours of the Target Time. Days in which the participant did not open the MEMS bottle due to out of the ordinary circumstances (e.g., hospitalization) will not be counted when computing the adherence rate. All participants will be given a MEMS log to write down such situations. In addition, at the second run-in visit, the RA will ask participants if there were any unusual circumstances that interfered with medication taking. At each MEMS reading visit, participants will be asked if the time(s) that they take their Target Medication have changed, and if so, the adherence rate for that particular reading will be adjusted accordingly.

Once it is established that the run-in adherence rate is <80% and the participant agrees, the RA will inform [name] that the participant should be randomized. Randomized participants will be instructed to put any refills for the Target Medication in the MEMS bottle.

2. Assignment of study identification numbers

Study identification numbers will be assigned immediately after enrollment. The identification number will consist of a 3 digit number chosen from a consecutive list. All data forms will also contain the participant's 3 initials (the first letter of the first, middle, and last names). If the participant has no middle name, an X will be used. Identification numbers and initials will be used to cross reference

CHAPTER 5: SCHEDULE AND OVERVIEW OF DATA COLLECTION

1. Overview

The Outcome Assessor will conduct assessments at baseline, and 6 and 12 months post-baseline masked to treatment assignment in participants' homes. Below we describe all of the study instruments. Table 2 describes how each measure will be used to assess the study aims.

2. Description of Study Measures

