Treatment Goals (PC-OT interventionist only)	- Description of each goal worked on during the course of the intervention - Plan for achieving goal - Goal Satisfaction Form - Strategies recommended (including devices/aids dispensed) - Referral made by OT - Extent of family/friend involvement for each recommended strategy	Intervention Visits

3. Follow up assessments

Follow-up assessments will be conducted by the OA. Monthly, the study coordinator will generate a computerized list of participants who are due for their follow-up assessments within the upcoming month. Included on the list will be the date of the last assessment for each participant as well as the ideal date that the assessment should take place. The date of the baseline in-home assessment will determine when the follow-up assessments should occur. For example, if the baseline assessment date was 7/31/14, ideally the 6-month assessment should take place on 1/31/15. Follow-up assessments should be timed so as to take place within 5 days of the ideal assessment date. For instance, in the above example, the 6-month assessment needs to occur anywhere from 1/26/15 through 2/5/15. If unforeseeable events prevent the follow-up assessment from occurring on time, an “Out of Window” form will be completed by the study coordinator and stored in the participant’s research chart.

4. Out of window policy

For any of the above described events that occur outside of the time window, an “Out of Window” form will be completed. The following information will be recorded on this form: Participant’s name and ID, the event that is out of window, the ideal date of the event as well as the actual date of the event, and the reason that the event is out of window.

Our goal is to have 80% of the assessment and treatment visits occur within the ideal time frame as specified above. We will produce monthly reports that delineate the percent of assessments and treatments that are occurring within the desired range. We will closely monitor these figures and develop corrective strategies as needed.

CHAPTER 6: QUALITY ASSURANCE AND MONITORING PROCEDURES

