Analyses: MEMS adherence data will be summarized as “percentage adherence” during each month. We will model the longitudinal trajectory of post-randomization adherence data using mixed effects linear regression. Fixed effects will be time, randomization assignment, time by randomization interaction, run-in phase adherence, age at randomization, and baseline HbA1c. Random intercept and time effects and an appropriate residual error covariance structure will be assumed to account for within-subject correlation. For purposes of this analysis, we will treat time categorically as a 4 level variable (months 1-3, months 4-6, months 7-9, and months 10-12). Thus, we will have 3 repeated measurements of adherence for each time period. Within this model, we will estimate the average adherence by randomization group during months 4-6 and months 10-12 and test for differences between groups. Supplemental adherence measures (i.e., Morisky Self-Report, Proportion of Days Covered) will be analyzed using a mixed effects model similar to that used for the continuous HbA1c analysis above.

Aim 4: Determine if increasing MEMS-adherence to an oral DM medication mediates PC-OT’s impact on HbA1c levels at 6 and 12 months.

Hypothesis: PC-OT will reduce HbA1c level to the extent that it increases MEMS-adherence to an oral DM medication at 6 and 12 months.

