cost-benefit of PC-OT vs. EUC based on best practices in applied health economic methods. The CBA will employ the payer perspective since its main purpose is to explore whether PC-OT results in a cost-offset to health insurers and plan sponsors. Specifically, the CBA will inform whether the net financial benefit of PC-OT vs. EUC is $\geq \$0$, i.e., that the *cost* of PC-OT is equal to or exceeded by its *financial benefits* at 6 and 12 months. Costs will include intervention costs (using the framework for behavioral intervention costs published by Drs. [name] and [name]) and net financial benefits (e.g., healthcare utilization related to DM). This exploratory cost analysis will help to develop more formal and comprehensive economic analyses if PC-OT proves effective.

CHAPTER 12: STUDY TIMELINE

We anticipate conducting 500 baseline assessments to identify and recruit 100 participants. Recruitment will take 20 months. We will conduct 25 assessments per month, and expect to enroll about 7 to 8 participants per month into the run-in phase. Of these, we will randomize 5 participants per month. Study start-up will take place during the first 6 months of the trial. During the start-up phase we will: (1) refine the educational materials to be distributed to all randomized subjects using components from NIH's "4 Steps to Manage your Diabetes for Life" and [name] "Project DECIDE" workbook; (2) hire and train study staff; (3) refine and implement procedures for study recruitment; (4) create study data bases; (5) create the randomization schedules; (6) develop the final version of study instruments and protocols; and (7) develop a comprehensive referral list for study interventionists.

The run-in phase will begin immediately after enrollment, and should be completed by month 28. For the 100 randomized participants, we will download MEMS data monthly for 12 months. We expect the collection of MEMS data to be completed by month 40. The 5 initial sessions of study treatment for both PC-OT and EUC participants will be completed by month 30. The 3 booster sessions will begin in month 13 and will continue through month 36. Six month follow-up assessments will take place month 13 through month 33. The 12 month follow-up assessments will begin in month 20 and will be completed by month 40. Months 41 through 48 will be devoted to data cleaning and analysis, and dissemination of study findings.

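### Visits are timed from the baseline home visit but MEMS months appear to run from randomisation, so part of the Aim 4 adherence mediator is recorded after the HbA1c it should explain

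*Combined protocol and SAP*

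**What the plan says.** **Visit clock.** The overview of Chapter 5 reads: "The Outcome Assessor will conduct assessments at baseline, and 6 and 12 months post-baseline masked to treatment assignment in participants' homes". Section 3 of that chapter fixes the origin: "The date of the baseline in-home assessment will determine when the follow-up assessments should occur". It adds: "Follow-up assessments should be timed so as to take place within 5 days of the ideal assessment date". A worked example with calendar dates follows.

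**What lies between baseline and randomisation.** Under Chapter 4, section 1, the Outcome Assessor will "schedule an in-home visit to obtain informed consent, administer the baseline assessment, and test the participant's A1c level". The next step is the eligibility check: "Within 1 week of this in-home visit, the PI will review" the neuropsychological profile. The research assistant then calls the participant, obtains pharmacy labels (no duration is given), makes a set-up visit and returns after a 2-week run-in. Randomisation follows the run-in.

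**Adherence clock.** Chapter 11, Aim 3 says: "We will model the longitudinal trajectory of post-randomization adherence data using mixed effects linear regression". Time is grouped into months 1-3, 4-6, 7-9 and 10-12, and run-in adherence is a separate covariate. Aim 4 uses adherence in months 4-6 as mediator for the 6-month HbA1c outcome. For the 12-month outcome it uses months 9-12, which it also describes as three months long.

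**Calendar.** Chapter 12 has run-in complete by study month 28 and MEMS collection complete by month 40. It also says "Six month follow-up assessments will take place month 13 through month 33" and "The 12 month follow-up assessments will begin in month 20 and will be completed by month 40".

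**The concern.** A mediator has to precede the outcome it is meant to explain. If visits are due 6 months after baseline while MEMS months start at randomisation, the last part of months 4-6 lies after the blood draw for every participant seen within the visit window. Adherence recorded after the draw cannot have influenced that HbA1c value. Including it mixes irrelevant data into the indirect effect, by an amount that differs from one participant to the next. I found nothing in the available text that aligns the two clocks.

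There is a second, lesser consequence. The primary time point is labelled 6 months, but time since randomisation at that visit is shorter than 6 months and not constant. The report should describe it as such.

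**Working it through.** **1. The plan's own example.** Baseline on 7/31/14 gives an ideal date of 1/31/15. Five days either side is 1/26/15 to 2/5/15, as Chapter 5 states. The visit clock is therefore unambiguous.

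**2. Origin of the MEMS months.** Month 1 is not explicitly defined. Two points support randomisation: Aim 3 describes the data as post-randomisation, with run-in adherence held separately as a covariate, and the Chapter 12 dates fit, since 28 + 12 = 40.

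**3. The gap, g, from baseline visit to randomisation.** The run-in alone sets a minimum of 2 weeks. Adding the full review week gives 3 weeks. The label step has no stated length, so 4 and 6 weeks are assumptions. Enrolment to month 26 (Table 1) and run-in completion by month 28 give 28 - 26 = 2 months, which is only a loose calendar bound.

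**4. Effect on timing.** With 30.44 days per month and g in months:
- time from randomisation to the 6-month draw = 6 - g
- time from randomisation to the 12-month draw = 12 - g
- share of MEMS months 4-6, the interval (3, 6], after the draw = g / 3

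| Gap | g (months) | 6-month draw | 12-month draw | Share of months 4-6 after draw |
|---|---|---|---|---|
| 2 weeks (minimum) | 0.46 | 5.54 | 11.54 | 15% |
| 3 weeks | 0.69 | 5.31 | 11.31 | 23% |
| 4 weeks (assumed) | 0.92 | 5.08 | 11.08 | 31% |
| 6 weeks (assumed) | 1.38 | 4.62 | 10.62 | 46% |
| 2 months (loose bound) | 2.00 | 4.00 | 10.00 | 67% |

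The 5-day tolerance does not remove the overrun. At the 2-week minimum with the visit 5 days late, (14 - 5) / 30.44 / 3 = 10% of the window still follows the draw.

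**5. The 12-month mediator.** The overrun is again g months. If the window is months 10-12, as in Aim 3, the shares are the same as above. Read literally, months 9-12 is four monthly values, although Aim 4 calls it three months.

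**6. HbA1c look-back and the session period.** Chapter 5 gives HbA1c a look-back of 2 to 3 months, and Chapter 1 has the five initial sessions spread over 3 months. Assume sessions start at randomisation and occupy (0, 3].
- 3-month look-back: (3 - g, 6 - g], which overlaps the sessions by g months.
- 2-month look-back: (4 - g, 6 - g], which overlaps only if g exceeds 1 month. The overlap is zero at 2, 3 and 4 weeks, and 1.38 - 1 = 0.38 months at 6 weeks.

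**7. Chapter 12 against the visit rule.** The 6-month and 12-month visits are 20 - 13 = 7 and 40 - 33 = 7 months apart, not 6. Timing from the last enrolment gives ends at 26 + 6 = 32 and 26 + 12 = 38. Timing from the last run-in gives 28 + 6 = 34 and 28 + 12 = 40. The stated ends are 33 and 40, so the pair fits neither clock.

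**The case against.** The strongest counter-argument is that timing visits from baseline is a defensible choice. The primary endpoint is a change from an HbA1c drawn at the baseline visit, and the written rule holds that interval at 6 months. Timing from randomisation would make it 6 months plus a variable gap. This stands, and it is why re-timing the visits is only an option in the fix.

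Several stronger readings are tempting and should not be drawn:
- **That the visit falls at 4 months.** This treats two planning limits as one participant's gap. Chapter 12 also says that run-in starts immediately after enrolment, and its other rows imply different last starts: initial sessions 30 - 3 = 27, last booster 36 - 10 = 26, 6-month visit 33 - 6 = 27, 12-month visit 40 - 12 = 28. The calendar is too coarse to yield an individual gap.
- **That Aim 3 has a temporal-order problem.** Aim 3 compares adherence between arms, and HbA1c enters only as a baseline covariate.
- **That the primary effect is diluted.** Overlap with the session period depends on the look-back length and the gap (step 6). Chapter 8 also says treatment addresses medication adherence first, so the session period need not be free of effect. If sessions start promptly, all five are finished before the visit even at 4 months.

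It is also fair to say that the MEMS origin is inferred. What remains is that, on the reading the text best supports, the mediator overruns its outcome even at the 2-week minimum.

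**Conclusion.** The point holds for Aim 4. Between 15% (the 2-week minimum) and 46% (an assumed 6-week gap) of the months 4-6 mediator is recorded after the 6-month blood draw, and the 12-month mediator overruns by the same number of months. This rests on MEMS month 1 starting at randomisation and on the assumed gaps, since the documents give no total.

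For the primary comparison, the draw falls about 4.6 to 5.5 months after randomisation over the same range of gaps, and the time varies between participants. A reader might infer bias between the arms. The documents do not support that, because the timing rule is the same for both. The matter for Aim 1 is accurate labelling of follow-up time. For Aim 4 the specified analysis should change.

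**What to change.** 1. **Aim 4.** Define the 6-month and 12-month mediators as the three MEMS months ending at the actual HbA1c draw date, counted back from the date-stamped openings. This also handles visits made out of window. Replace months 9-12 with a three-month window consistent with Aim 3.
2. **MEMS clock.** State randomisation as the origin of MEMS month 1. The Aim 3 periods can then stay as written.
3. **Calendar.** Reconcile the 6-month and 12-month visit ranges in Chapter 12 with the due-date rule in Chapter 5, so that they are 6 months apart.
4. **Boosters.** The available text does not say which clock booster months 6, 8 and 10 follow. The passages must be reconciled on this.
5. **Optional.** Time the 6- and 12-month visits from randomisation. Both clocks would then agree to within the 5-day window, but the interval from the baseline HbA1c would become 6 or 12 months plus a variable gap. The last 12-month visit would still fall by month 40; the last 6-month visit would move from month 33 to 34.

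Items 1 to 4 need only wording and a small change to the derivation of the mediator from data already collected. Item 5 also changes the coordinator's due-date list.

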2.1. Hardware

Computers will be purchased for project staff, and they will be password protected and encrypted. All computers will be serviced by the IT department at Thomas Jefferson University.

2.2. Software

All data will be managed and analyzed with SAS, SPSS, or Mplus. Teleform will be used to create all data forms. It will also be used for direct data entry and scanning hard copies of data. Both the project director and the OA will have individual licenses. We purchase annual support contracts for Teleform.

3. Distribution of blank forms

All assessment data will be entered directly onto the OA's laptop, eliminating the need for blank forms. The OA will, however, bring blank hard copies of assessment forms to all assessment visits should the laptop malfunction. Electronic copies of all forms will be stored on the study network (which is maintained by Jefferson). Intervention forms will be distributed to the interventionists as they are needed.

4. Participant identification and confidentiality

Participant identifiers will be assigned immediately after enrollment, and will be used on all data forms. Neither participant names, nor any other identifying information other than the identifiers, will ever be on the data forms. All hard copies of participant information (data forms, contact information, signed informed consents, randomization sheets, etc.) will be stored in locked file cabinets stored in the PI's lab. Each participant will have 2 charts, and each will be stored in separate file drawers. The following will be stored in the participant identification chart: the participant's contact information, data collected at screening, the signed consent forms, the randomization sheet, copies of medication labels, pharmacy refill records, and serious adverse event/alert documentation. The following will be stored in the participant data chart: all hard copies of assessment forms, intervention forms, notes, withdrawal forms, and out of window forms. None of the documents contained in the data chart will have the participant's name. A master list linking participant name with identifier will be stored in an encrypted password protected file on the project director's computer.

5. Linking participant records

The only data base that will contain both participant names and identifiers is the tracking list which will be accessible to the PI, the project director, and the study coordinator. All other data bases will identify individual participants by their unique identifiers. Assessments completed at different time points will be stored in separate data bases. Unique identifiers will be used to link data obtained from participants at different time points.

6. Procedures for data checking and editing

Data forms (screens, all assessment batteries, intervention notes) will be reviewed within 1 week of completion. This review is performed to check that all information is accurate, check marks or circled answers are clearly demarcated (if completed on a hard copy), and that each item is completed. Staff also checks to assure that each page of the IRB participant consent form is initialed and the participant's signature is obtained on the final page of the consent.

All changes to data are submitted via a data edit request form for review and signature by the PI. Data edits are entered directly into the respective data bases. The data edit request form will be stored in the participant's chart. A data base will be maintained that documents each data edit, including the date of the edit as well as the type of change that was made.

7. Description of data edits

Each month the project director will generate a report documenting the number and type of data edits performed for the previous month. We expect few data edits as data entry errors will be minimal due to direct entry. Most edits will consist of changes in participant contact information.

8. Internal data quality monitoring

Data quality monitoring will be minimal, owing to the use of Teleform. Since all data will be entered directly into the computer or scanned, there will be no data entry errors. To insure data integrity, weekly, the project director will produce frequency distributions on all assessment data. This will highlight out of range values. In the event that this occurs, the project director will inform the OA, and a data edit request form will be completed accordingly.

9. Communication related to data collection

Weekly, the study coordinator will generate assessment schedules for the study assessor that will indicate which participants are due for follow-up assessments, MEMS data downloads, or booster intervention sessions in the upcoming 2 weeks. On a monthly basis, the study coordinator will produce reports that will indicate the number of participants who: (1) were approached for study participation; (2) were screened for study eligibility; (3) were enrolled in the study; (4) had an assessment at each time point; and (5) withdrew from the study (and the reason for withdrawal). This report will also indicate the number of assessments that occurred out of window, the number and type of protocol deviations, the number of participants who became unmasked, and the percent of missing data.

10. Missing data

Missing data are entered according to the following established coding scheme: (1) NA = 99; and (2) refused = 88.

11. Data back up

Data files are entered and stored on a secure network maintained by TJU. An additional full-drive backup is completed monthly.

12. Data collection and transition

All in-home assessments will be entered directly on a laptop computer. The OA will always bring an extra laptop battery as well as a blank hard copy of the assessment form to the participants' homes. This will enable all data to be collected should the computer malfunction. It is very important that all fields on all assessment forms are filled in (unless otherwise noted). If the participant is unable to respond to a particular item, or if it is not applicable, the OA will check NA for forced choice questions, or write "NA" for open-ended questions. Immediately after completing the in-home assessment, the OA will check the assessment forms to insure that all

information is complete. If there is any missing data, the OA will call the participant in order to obtain complete information.

13. Equipment protection

All study computers will be maintained by the Technical Assistance Center at Thomas Jefferson University. The Technical Assistance Center assumes responsibility for the installation and repairs of all computers. All data are backed up in triplicate every day, so in the event of a malfunction, all data will be preserved.

All MEMS caps and bottles, as well as the software to read the data from the MEMS caps, will be supplied by the Aardex group. The Aardex group has a full support system available should the caps or software malfunction.

CHAPTER 11: DATA ANALYSIS

We will use descriptive statistics and bivariate comparisons of participants by treatment group to characterize the sample, assess randomization success and the impact of attrition, and check data quality. We will use an intent-to-treat approach for all analyses in that we will include all participants with follow-up data regardless of the extent to which they received treatment. For longitudinal analyses we will include all available data from all participants. We account for attrition by assuming that any missing data are missing at random, and apply models that yield valid estimates under this assumption. For analysis of continuous outcomes, we will check assumptions of normality and homoskedasticity of errors using model residuals. If necessary, we will transform outcomes as appropriate prior to analysis. We will present all model-derived estimates with 95% confidence intervals, and will use SPSS, SAS, and Mplus software as appropriate.

Aims 1 and 2: Test the efficacy of PC-OT to reduce HbA1c level by 0.5% at 6 months (Aim 1) and at 12 months (Aim 2).

Hypotheses: 55% of PC-OT-treated participants, compared to 25% of EUC controls, will have a reduction in HbA1c of 0.5% at 6 months (short term effect) and 12 months (maintenance effect).

Analyses: At each outcome measurement (6 and 12 months), we will categorize participants as having achieved this outcome or not. We will jointly model this dichotomous outcome at 6 and 12 months using Poisson regression within a generalized estimating equation (GEE) framework. The model will include time (6 months, 12 months), randomization assignment, time by randomization interaction, the stratification variable (baseline HbA1c), age, and baseline MEMS adherence (from the Run-in Phase). This model allows for direct estimation of the relative risk at each follow-up time while accounting for correlation among repeated measures from the same participant. We will consider participants who start insulin during the trial as not having a meaningful reduction in HbA1c, regardless of the actual level at 6 and 12 months. From the model, we will calculate model-adjusted estimates for incidence of HbA1c reduction in each arm at 6 months, as well as the adjusted estimate of the relative risk. We will evaluate the primary hypothesis by testing the null hypothesis that the relative risk at 6 months = 1. For Aim 2, we will calculate the relative risk at 12 months from the same model, and evaluate the hypothesis by testing the null hypothesis that the relative risk at 12 months = 1.

We will also model HbA1c level as a continuous outcome to estimate the average change over time in each treatment group. We will use mixed effects linear regression to jointly model HbA1c at baseline, 6 months, and 12 months. Fixed effects will be time (baseline, 6 months, 12 months), randomization assignment, time by randomization interaction, age at randomization, and baseline MEMS-adherence from the run-in phase. A random intercept term and an appropriate covariance structure will be used to account for correlation among repeated measurements. Within this model we will estimate the average change in HbA1c by group from baseline to 6 months, and from 6 months to 12 months. We will compare groups with respect to average change over these two time periods as an additional estimate of the effect of PC-OT compared with EUC.

Aim 3: Test the efficacy of PC-OT to increase MEMS-measured adherence to an oral DM medication at 6 and 12 months.

Hypothesis: PC-OT will increase MEMS-measured adherence to a greater extent than EUC at 6 and 12 months.

Analyses: MEMS adherence data will be summarized as “percentage adherence” during each month. We will model the longitudinal trajectory of post-randomization adherence data using mixed effects linear regression. Fixed effects will be time, randomization assignment, time by randomization interaction, run-in phase adherence, age at randomization, and baseline HbA1c. Random intercept and time effects and an appropriate residual error covariance structure will be assumed to account for within-subject correlation. For purposes of this analysis, we will treat time categorically as a 4 level variable (months 1-3, months 4-6, months 7-9, and months 10-12). Thus, we will have 3 repeated measurements of adherence for each time period. Within this model, we will estimate the average adherence by randomization group during months 4-6 and months 10-12 and test for differences between groups. Supplemental adherence measures (i.e., Morisky Self-Report, Proportion of Days Covered) will be analyzed using a mixed effects model similar to that used for the continuous HbA1c analysis above.

Aim 4: Determine if increasing MEMS-adherence to an oral DM medication mediates PC-OT’s impact on HbA1c levels at 6 and 12 months.

Hypothesis: PC-OT will reduce HbA1c level to the extent that it increases MEMS-adherence to an oral DM medication at 6 and 12 months.

Analysis: We will use structural equation modeling (SEM) to evaluate this aim. We will simultaneously model the dichotomous HbA1c reduction variable at 6 and 12 months, and adherence data at months 4-6 and 9-12. Adherence at months 4-6 (and 9-12) will be reduced to a latent variable representing the average adherence over the three month period. HbA1c will be modeled using a probit link. The model we will fit has paths from treatment to HbA1c reduction at 6 and 12 months (direct effects), treatment to adherence at 6 and 12 months, adherence at 6 months to HbA1c reduction at 6 months, and adherence at 12 months to HbA1c reduction at 12 months. Using MPlus software, we will fit the SEM model and follow the strategy outlined in Muthén (2011) to calculate the total indirect effect for adherence at 6 months and at 12 months. Adherence is considered a mediator of the effect of treatment on reduced HbA1c if there is a significant path from treatment through adherence to HbA1c (i.e., an indirect effect). Standard errors and confidence intervals will be calculated using bootstrapping. We will perform a similar analysis to explore whether changes in Diabetes Self-Care Inventory-Revised scores [a measure of diabetes self-management (e.g., diet, exercise)] also mediate the effect of treatment on HbA1c reduction.

Exploratory Aims:

1) Evaluate if PC-OT over 12 months: a) improves other DSM practices (e.g., diet, exercise); b) reduces emergency room visits and hospitalizations; c) prevents declines in cognition, function, and depression; and d) improves quality of life.

Analyses: We will evaluate continuous outcomes using the mixed effect model outlined for HbA1c. Count outcomes (e.g., number of ER visits) will be evaluated using repeated measures Poisson regression using GEE.

2) Evaluate PC-OT’s costs and net financial benefits: This economic analysis will consist of an exploratory cost-benefit analysis (CBA) based on cost and outcome data. We will calculate the Version 4 (Jan 2015)

cost-benefit of PC-OT vs. EUC based on best practices in applied health economic methods. The CBA will employ the payer perspective since its main purpose is to explore whether PC-OT results in a cost-offset to health insurers and plan sponsors. Specifically, the CBA will inform whether the net financial benefit of PC-OT vs. EUC is $\geq \$0$, i.e., that the *cost* of PC-OT is equal to or exceeded by its *financial benefits* at 6 and 12 months. Costs will include intervention costs (using the framework for behavioral intervention costs published by Drs. [name] and [name]) and net financial benefits (e.g., healthcare utilization related to DM). This exploratory cost analysis will help to develop more formal and comprehensive economic analyses if PC-OT proves effective.

CHAPTER 12: STUDY TIMELINE

We anticipate conducting 500 baseline assessments to identify and recruit 100 participants. Recruitment will take 20 months. We will conduct 25 assessments per month, and expect to enroll about 7 to 8 participants per month into the run-in phase. Of these, we will randomize 5 participants per month. Study start-up will take place during the first 6 months of the trial. During the start-up phase we will: (1) refine the educational materials to be distributed to all randomized subjects using components from NIH's "4 Steps to Manage your Diabetes for Life" and [name] "Project DECIDE" workbook; (2) hire and train study staff; (3) refine and implement procedures for study recruitment; (4) create study data bases; (5) create the randomization schedules; (6) develop the final version of study instruments and protocols; and (7) develop a comprehensive referral list for study interventionists.

The run-in phase will begin immediately after enrollment, and should be completed by month 28. For the 100 randomized participants, we will download MEMS data monthly for 12 months. We expect the collection of MEMS data to be completed by month 40. The 5 initial sessions of study treatment for both PC-OT and EUC participants will be completed by month 30. The 3 booster sessions will begin in month 13 and will continue through month 36. Six month follow-up assessments will take place month 13 through month 33. The 12 month follow-up assessments will begin in month 20 and will be completed by month 40. Months 41 through 48 will be devoted to data cleaning and analysis, and dissemination of study findings.

Year 1 (7/1/14 – 6/30/15)						Year 2 (7/1/15 – 6/30/16)						Year 3 (7/1/16 – 6/30/17)						Year 4 (7/1/17 – 6/30/18)					
2	4	6	8	10	12	14	16	18	20	22	24	26	28	30	32	34	36	38	40	42	44	46	48
START UP																							
			BASELINE ASSESSMENTS (N = 500)																				
			RUN IN PHASE FOR PARTICIPANTS WITH MCI AND HbA1C \geq 7.5 (N = 150)																				
			RANDOMIZATION (N = 100)																				
			MONTHLY COLLECTION OF MEMS DATA FOR RANDOMIZED PARTICIPANTS (N = 100)																				
